5.6. Randomization Errors

Patients who were randomized from an incorrect stratum will be identified by comparing the strata recorded on the RTSM system (Randomization and Trial Supply Management)/randomization CRF page with the strata derived from screening data. A listing of patients who were randomized from an incorrect stratum will be presented. The randomized stratum (from RTSM system/randomization CRF) rather than actual stratum (derived from screening data) will be used for all the efficacy analyses. A sensitivity analysis will be performed using the actual stratum on the primary endpoint if the discrepancy rate is greater than 5% in the final result.

5.7. Other Key Definitions and Computations

Study Day

Study day will be calculated in reference to the date of the first dose (Study Day 1, which refers to the enrollment/randomization in the protocol). For assessments conducted on or after the first dose date, study day is calculated as (assessment date – first dose date + 1). For assessments conducted before the first dose date, study day is calculated as (assessment date – first dose date). There will be no Study Day 0.

In the listings, study days will be presented along with assessment date where applicable.

Date of First Dose and Date of Last Dose of Study Drug

The date of the first dose of study drug is defined as the date a patient receives the first dose of study drug (roxadustat or placebo). The date of the last dose of study drug is defined as the date a patient receives the last dose of study drug (roxadustat or placebo).

Treatment Day

Treatment day will be calculated in reference to the date of the first dose of study drug. Treatment Day 1 corresponds to the date a patient receives the first dose of study drug. For assessments conducted on or after the date of the first dose of study drug, treatment day will be calculated as (assessment date – date of first dose of study drug + 1). There will be no Treatment Day 0.

Treatment Period

The treatment period is defined as the period of time from the date and time of the first dose of study drug through the date of last dose.

6. PATIENT ENROLLMENT AND DISPOSITION

6.1. Eligibility Criteria

Eligibility criteria will be summarized for all screened subjects in open-label component and double-blind component. The data will be summarized with respect to:

- number of subjects screened
- number (%) of subjects screen-failed
- number (%) of subjects for each failed inclusion/exclusion criterion

Subject level inclusion criteria not met/exclusion criteria met listings will be provided.

6.2. Subject Accountability and Disposition

For open-label component, patient disposition will be summarized by dose level cohort and overall. For OL high-erythropoietin component, the summaries will be presented along with the cohorts from open-label component. For double-blind component, patient disposition will be summarized by treatment group and overall.

The data will be summarized with respect to:

- number of patients screened,
- number (%) of patients screen-failed (and by major reason),
- number of patients enrolled (defined as patients who signed informed consent form and received treatment assignment),
- number (%) of patients randomized, not treated (double-blind component),
- number (%) of patients randomized, treated (double-blind component),
- number (%) of patient completed study treatment (Note: for 28-week analysis, the summary will use the data in the first 28 weeks of treatment period),
- number (%) of patients prematurely discontinued from study treatment by specific reason as recorded on the CRF,
- number (%) of patients prematurely discontinued from the study by specific reason as recorded on the CRF.

Percent of screen-failed will be based on the number of patients screened. All other percentages for patients will be based on the number of patients enrolled.

In addition, the number and percentage of patients included in the FAS, PPS and SAF will be summarized. Percentage will be based on the number of patients enrolled.

Number and percentage of subjects with early discontinuation of study medication by demographics and baseline characteristics will be summarized in the SAF.

Consort diagrams describing the disposition of patients in the SAF will be provided.

All patients who prematurely discontinued from treatment or study will be listed by discontinuation reason.

7. PROTOCOL DEVIATIONS

Important protocol deviations of interest may include, but are not limited to, the following:

- Patients who did not meet inclusion/exclusion criteria
- Patients who received disallowed concomitant medications or non-drug therapy during study treatment period
- Patients who took IV iron while on study

The number and percentage of important protocol deviations will be categorized and tabulated as appropriate. A subset of pre-specified major protocol deviations will exclude some patients in the PPS analyses. These will be identified prior to database lock and study unblinding. Considerations will be given according to the following table. The number and percentage of major protocol deviations will be categorized and tabulated as appropriate.

Table 2: Criteria for Assessing Major Protocol Deviations Table

Number	Major Protocol Deviation
1	Violation of inclusion or exclusion criteria which may affect the assessment of the efficacy of the study drug
2	Administration of prohibited concomitant medication or non-drug therapy
3	Significant noncompliance with study procedures, e.g., a patient skipping consecutive scheduled assessments, will be evaluated case by base
4	Developed criteria for discontinuation of study drug but did not discontinue study drug treatment
5	Received the wrong treatment or incorrect dose resulting in any adverse event
6	Were incorrectly stratified by the study investigators

8. DEMOGRAPHICS AND OTHER BASELINE CHARACTERISTICS

For categorical data, frequencies and percentages will be provided and, for continuous data, descriptive statistics, including sample size (n), mean, median, standard deviation, and range of values (i.e., minimum and maximum values) will be provided. All information to be summarized will also be presented in listings.

Comparability of baseline characteristics among treatment groups will be tested using analysis of variance (ANOVA) model for continuous variables and Chi-Square test (or Fisher's exact test if cell count < 5) for categorical variables for reference only. The p-values are exploratory and no formal statistical inference will be made.

For open-label component, the summaries will be presented by dose level cohort and overall using safety population. For OL high-erythropoietin component, the summaries will be presented along with the cohorts from open-label component using safety population. For double-blind component, the summaries will be presented by treatment group and overall using FAS, Safety and PPS. The following baseline characteristics will be summarized and listed:

- age
- age group (< 65 / >= 65 years)
- sex
- ethnicity
- race
- weight
- baseline Serum EPO level
- baseline Serum EPO level category [<200 (IU/L), 200-400 (IU/L), >400 (IU/L)]
- serum EPO level category based on actual strata [<200 (IU/L), 200-400 (IU/L)]
- pRBC-transfusion burden at baseline
- baseline pRBC-transfusion burden group (1 pRBC/8-weeks vs. 2-4 pRBC/8-weeks over 16 consecutive weeks)
- pRBC-transfusion burden based on actual strata (1 pRBC/8-weeks vs. 2-4 pRBC/8-weeks over 16 consecutive weeks)
- baseline ECOG performance status
- MDS duration (based on medical history)
- WHO Classification of MDS
- pre-transfusion hemoglobin (Hb) at baseline
- baseline platelet counts
- cytogenetic actual category
- Anticoagulants use at baseline (Yes/No) - if applicable.
- bone marrow blast
- IPSS-R risk category (low risk / very low risk vs. intermediate risk classification)

- eGFR
- baseline C-reactive protein (CRP)
- CRP group (CRP \leq ULN vs. CRP > ULN)
- Ferritin and Ferritin group (< 100 ng/mL, \geq 100 ng/mL and < 400 ng/mL, \geq 400 ng/mL)
- TSAT and TSAT group (< 20%, \geq 20% and < 40%, \geq 40%),
- iron repletion status ([TSAT <20% or ferritin < 100 ng/mL] vs. others)

MDS duration will be calculated from the earliest date documented on the medial history CRF to Day 1.

9. MEDICAL HISTORY

Medical history will be coded using the Medical Dictionary for Regulatory Activities (MedDRA, version 19.1). A summary table will be presented by system organ class (SOC) and preferred term (PT).

For open-label component, the summaries will be presented by dose level cohort using safety population. For OL high-erythropoietin component, the summaries will be presented along with the cohorts from open-label component using safety population. For double-blind component, the summaries will be presented by treatment group using FAS.

10. EXTENT OF EXPOSURE TO STUDY MEDICATION

Extent of exposure, treatment compliance and dose modification will be summarized for the safety population.

For open-label component, the summaries will be presented by dose level cohort. For double-blind component, the summaries will be presented by treatment group. For extent of exposure and treatment compliance, the summaries will be presented up to Week 28 and Week 52/EOT separately. For OL high-erythropoietin component, the summaries will be presented along with the cohorts from open-label component.

10.1. Extent of Exposure

Exposure to study medication will be summarized in terms of treatment duration, which is calculated as the number of weeks from the date of first study medication taken to the date of last dose taken, inclusively.

Duration (in weeks) = (date of last dose - date of first dose + 1) / 7

Total actual dose (in mg or mg/kg) for dose interval k is calculated as

*dose strength in interval k * (last day of dose interval k - first day of dose interval k + 3 days) * (frequency for dose interval k/7)*

The first and last day of dose interval will be obtained from IP dosing form. The first day of dose interval k is the first date of a new dosing level. For example, the dose of 50 mg TIW starts on 01/07/2017, ends on 02/10/2017, the total dose is $50 * (33 + 3) * (3/7) = 771.4$ mg. The average weekly dose is calculated as the sum of all actual doses over the treatment period (in mg) divided by actual exposure duration (in weeks) during the period. The average weekly dose per weight is calculated as the sum of all actual doses over the treatment period per weight (in mg/kg) divided by actual exposure duration (in weeks) during the period.

Duration of exposure and average weekly exposure over time will be tabulated for the safety population. Exposure duration by category (<2 weeks, 2 weeks - <8 weeks, 8 weeks - <=28 weeks) will be summarized for Week 28 analysis. Subject exposure over time (probability of subjects still on treatment) up to Week 28 and up to Week 52 will be plotted by treatment groups.

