### **5.4 Route of Administration and Dose**

#### **5.4.1 Roxadustat/Placebo**

All patients will take doses TIW for the entire duration of the study. Roxadustat/placebo will be dispensed to patients with instructions for self-administration of the tablets orally on each dosing day, according to the dosing schedule. The tablets are to be swallowed whole. Tablets should not be cut.

First dose of roxadustat /placebo should be administered on Day 1 after completion of all procedures including laboratory draws. Study drug doses should be administered at least 2 days apart, and no more than 4 days apart. Dosing should occur at approximately at the same time of day. Roxadustat/placebo can be taken with water and with or without food.

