- The proportion of patients who achieve a mean Hb increase of ≥ 1.5 g/dL averaged over any 8 weeks

The denominator for the proportions is FAS population.

Similar methods will be used as in [Section 12.3.1.1](#).

Mean (\pm SE) Hb (g/dL) from Baseline to Week 28 and to Week 52 will be plotted by treatment groups.

12.3.4.5. Impact of baseline endogenous erythropoietin levels on roxadustat treatment response and dose requirement

TI response rate (RBC TI at least ≥ 8 weeks) will be analyzed by baseline endogenous EPO level (< 200 mIU/mL **OR** > 200 mIU/mL and ≤ 400 mIU/mL) using the methods described in [Section 12.3.1](#). A summary table will be provided. See [Section 12.3.3.1](#) for the detail of definition of TI response.

Average weekly exposure data will be analyzed by baseline endogenous EPO level and treatment group.

The average weekly dose will be analyzed by baseline endogenous EPO level (< 200 mIU/mL **OR** > 200 mIU/mL and ≤ 400 mIU/mL) and treatment group.

In order to compare patients with baseline endogenous EPO level < 200 mIU/mL to patients with baseline endogenous EPO level > 200 mIU/mL and ≤ 400 mIU/mL), the ANCOVA with baseline Hb value as covariate and baseline endogenous EPO level as class category.

RBC TI response analysis as primary efficacy endpoint will be repeated for each level of baseline EPO: ≤ 100 , ≤ 200 , ≤ 300 and, ≤ 400 mIU/mL.

Proportion of patients who achieve a mean Hb increase of ≥ 1.0 g/dL and ≥ 1.5 g/dL (averaged over 8 weeks in those that achieved TI) compared to pre-transfusion Hb at baseline will be summarized for each level of baseline EPO: < 200 mIU/mL **OR** > 200 mIU/mL and ≤ 400 mIU/mL.

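### SAP 10.1: the average weekly dose counts three end days in the dose total but one in the duration, so an exact three-times-weekly taker averages more than three doses a week; the worked example is also one day short

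*SAP*

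**What the plan says.** SAP 10.1 (Extent of Exposure) gives three linked definitions.

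- Treatment duration: "Duration (in weeks) = (date of last dose - date of first dose + 1) / 7".
- Total actual dose for an interval: dose strength, times a day count, times frequency/7. The day count is "last day of dose interval k - first day of dose interval k + 3 days".
- Average weekly dose, in mg and in mg/kg: the sum of the interval totals "divided by actual exposure duration (in weeks) during the period". No other duration is defined for this ratio.

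The section illustrates the total with a case in which "the dose of 50 mg TIW starts on 01/07/2017, ends on 02/10/2017", and evaluates it as "50 * (33 + 3) * (3/7) = 771.4" mg.

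Average weekly exposure is tabulated for the safety population. It is used again in SAP 12.3.4.5, on dose requirement: "The average weekly dose will be analyzed by baseline endogenous EPO level" and by treatment group, and an ANCOVA comparing the two EPO groups is specified there.

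Protocol 5.4.1 sets the dosing pattern: "All patients will take doses TIW for the entire duration of the study", and "Study drug doses should be administered at least 2 days apart, and no more than 4 days apart".

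**The concern.** A weekly average should return three doses a week for a patient who takes exactly three doses a week. Here the numerator covers two more days than the denominator for every single-level patient, so it cannot. Because the two days are fixed, the relative error depends on how long the patient was treated. It therefore differs between patients and need not cancel when groups are compared. SAP 10.1 itself reports exposure under 2 weeks and from 2 to under 8 weeks, where two extra days weigh most.

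The example matters for a practical reason. A programmer who checks code against it will see a mismatch, and may alter correct code to reproduce a wrong figure.

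**Working it through.** **The plan's own figure.** The printed arithmetic is right as arithmetic: 50 × (33 + 3) × 3/7 = 771.4 mg. The input of 33 does not follow from the dates.

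- Read as month/day: 7 to 31 January is 24 days, plus 10 days in February, so last minus first = 34.
- Read as day/month (1 July to 2 October 2017): 30 + 31 + 30 + 2 = 93.
- The value 33 arises only if both end dates are excluded or every month is given 30 days. Neither is the stated rule.

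With 34 days the SAP formula gives 50 × (34 + 3) × 3/7 = 792.9 mg. The printed total is 21.4 mg (2.7%) too low.

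**The ratio, one dose level.** Let D = last − first + 1 days.

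- Doses credited in the numerator: (D + 2) × 3/7.
- Weeks in the denominator: D/7.
- Doses per week: 3(D + 2)/D, an excess of 2/D over three.

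| D (days) | Excess 2/D |
|---|---|
| 14 | 14.3% |
| 28 | 7.1% |
| 56 | 3.6% |
| 196 | 1.0% |

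**The example carried through.** D = 35 days, or 5.0 weeks. The prescribed amount is 3 × 50 = 150 mg/week.

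- SAP formula with the correct day count: 792.9/5.0 = 158.6 mg/week (+5.7%, which is 2/35).
- SAP's printed total: 771.4/5.0 = 154.3 mg/week (+2.9%). The day-count slip hides half of the excess.
- Plus 3 in both parts: 792.9/(37/7) = 150 mg/week.
- Plus 1 in both parts: 50 × 35 × 3/7 = 750 mg, and 750/5.0 = 150 mg/week.

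The SAP does not compute a weekly average for this example; these four are derived from its definitions.

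**Several dose levels.** SAP 10.1 takes actual intervals from the dosing form and does not say on which day an interval ends when the level changes.

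- If each interval runs to the day before the next begins, each of K intervals adds two days and the excess is 2K/D. Four levels over 196 days give 8/196 = 4.1%.
- If each interval ends on the last dose taken at that level and the next starts g days later, each change adds 3 − g days. With g from 2 to 4 (Protocol 5.4.1) that is between −1 and +1 day per change, so the excess stays near 2/D.

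**Compliance.** SAP 10.2 uses plus 3 for prescribed dose, matching the plus 3 for actual dose in 10.1, so this mismatch does not arise there.

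**The case against.** The strongest reply is that this is a convention and not an error. The numerator estimates doses, not time. On a Monday/Wednesday/Friday pattern (an assumed schedule), last − first = 7w − 3 after w weeks, so plus 3 gives exactly 3w doses. The denominator is first to last dose inclusive, which is how the SAP defines exposure. Three real doses from Monday to Friday over 5/7 of a week also give 4.2 a week, even from perfect tablet counts. Part of this stands: the plus 3 is sound as a dose count, and plus 1 is sound as a reported duration. What does not stand is dividing one by the other and calling the result a weekly dose, since either convention used in both parts returns exactly three.

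A reader might infer that groups with more early stops will appear to need a higher dose. The documents do not support that. Patients who stop before 8 weeks will usually not have been escalated. In Protocol Appendix C one level up from approximately 2.5 mg/kg, the double-blind starting level in SAP 3.1, goes from 150 to 200, 200 to 250 or 250 to 300 mg. That is 20% to 33%, against an artefact of a few percent from 8 weeks on. Nothing indicates that early stopping differs by EPO group.

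Nor does the excess always grow as exposure shortens. With back-to-back intervals, four levels over 196 days (4.1%) exceeds one level over 56 days (3.6%).

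**Conclusion.** The formula is wrong as written, and the effect is small. For one dose level the average weekly dose of an exact taker is overstated by 2/D, about 14% at 14 days, 3.6% at 56 and 1.0% at 196; this needs no assumption about dosing weekdays. The 2K/D figure for several levels rests on intervals being contiguous, which SAP 10.1 leaves open. The example's day count is wrong under either reading of the dates.

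The reach is limited to descriptive exposure summaries and the exploratory analysis by baseline EPO, whose p-values SAP 12.3.4 treats as nominal. The primary endpoint and the gatekept secondary endpoints do not use this quantity. The direction of any between-group distortion cannot be determined from the documents.

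**What to change.** In SAP 10.1, make the total days in the numerator of the average weekly dose (mg and mg/kg) equal the days in its denominator:

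- Divide by (last dose − first dose + 3)/7.
- State on which day a dosing-form interval ends. Where intervals are contiguous, use plus 1 for every interval except the last, which keeps plus 3; the interval days then sum to last − first + 3. Changing the denominator alone would not be enough: with four contiguous levels over 196 days, 204/198 − 1 = 3.0% of excess would remain out of 4.1%.
- Alternatively, divide by the sum of the interval day counts used in the numerator. This leaves out any time between intervals, such as a hold, so the SAP should say whether that is intended.

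Leave the reported treatment duration unchanged. Correct the example to 34 days: 50 × (34 + 3) × 3/7 = 792.9 mg.

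The cost is one formula, one sentence on interval ends and one example. No new data are needed.

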10.2. Treatment Compliance

Study medication compliance will be calculated as the total amount of doses actually administered during that period divided by the total amount of doses prescribed expected to be taken during the same period (e.g. Day1 to Last dose) multiplied 100.

Total prescribed dose (in mg or mg/kg) for dose interval k is calculated as

*dose strength in interval k * (last day of dose interval k - first day of dose interval k + 3 days) * (frequency for dose interval k/7)*

The first and last day of dose interval will be obtained from Study Drug Dispensation form. The first day of dose interval is the first day of a new prescribed dosing level. The last day of dose interval is the day before the initial day of the next new prescribed dosing level, if it is the last dosing level, the last day of this dosing level will be the last treatment day.

If there is a dose interruption period and the reason is "PI decision", the amount of doses in the interruption period should be excluded from both the numerator and the denominator in the compliance calculation.

Descriptive statistics for study medication compliance will be presented by treatment group. A frequency summary of treatment compliance category (<75%, ≥75% to < 85%, ≥85% to ≤ 100% and >100%) will also be provided.

Date of first/last dose, duration of treatment, dates of discontinuation of treatment and study, and reason for study drug discontinuation will be listed for patients who discontinued the study drug prematurely.

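### SAP 10.2 adds 3 days to prescribed intervals that already run to the day before the next dose level, overstating prescribed drug by about 2 days per dose change; the 10.1 example also miscounts its days

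*SAP*

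**What the plan says.** SAP 10.2 defines compliance as drug administered "divided by the total amount of doses prescribed expected to be taken during the same period", times 100. Prescribed drug in interval k is the strength times ("last day of dose interval k - first day of dose interval k + 3 days") times the weekly frequency over 7. For levels followed by another level, the end date is fixed: "The last day of dose interval is the day before the initial day of the next new prescribed dosing level". For the final level, "if it is the last dosing level, the last day of this dosing level will be the last treatment day".

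SAP 10.1 uses the same expression, with the same 3 days, for drug actually taken. There, "The first and last day of dose interval will be obtained from IP dosing form". The section then defines the first day but not the last. Its example reads "the dose of 50 mg TIW starts on 01/07/2017, ends on 02/10/2017, the total dose is" 50 × (33 + 3) × (3/7) = 771.4 mg.

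Dosing is three times weekly: "All patients will take doses TIW for the entire duration of the study" (Protocol 5.4.1). The same section requires doses to be 2 to 4 days apart.

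Compliance is reported by treatment group with cuts at 75, 85 and 100% (SAP 10.2), up to Week 28 and up to Week 52/EOT (SAP 10). The exposure and compliance table is on the Week 28 list in SAP Appendix 19.9.

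**The concern.** A fixed constant in a days-times-frequency formula is right for only one type of end date. Three days fits an interval that stops on the last dose of a treatment week, because it completes the calendar week. An interval that runs to the eve of the next level is already complete and needs only the usual +1.

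SAP 10.2 joins the +3 to the second type of end date, so expected drug is too large for each level that is followed by another. The excess grows with the number of dose changes. Those changes depend on transfusions and hemoglobin (SAP 10.3), so the distortion is tied to response and need not be equal in the two arms. What is at stake is the accuracy of the compliance summary or, depending on how the dosing form is completed, of the exposure summary. The miscounted example adds a practical problem: a programmer who checks code against it will either fail to match or copy the error.

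**Working it through.** **1. The printed example.** The printed expression reproduces: 50 × (33 + 3) × 3/7 = 771.4 mg. The printed dates do not give 33.
- Month/day order, 7 January to 10 February 2017: 24 + 10 = 34 days, so the SAP's formula gives 50 × (34 + 3) × 3/7 = 792.9 mg.
- Day/month order, 1 July to 2 October 2017: 93 days, so date order does not explain the 33.
- If 02/10/2017 is the day before a new level, the interval is 34 + 1 = 35 days, or 35 × 3/7 = 15 doses, which is 750 mg.

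**2. Where +3 is right.** On a Monday/Wednesday/Friday schedule (assumed; it meets the 2-to-4-day spacing), one week from first to last dose is 4 days. Then 4 + 3 = 7 days and 7 × 3/7 = 3 doses. This suits an interval ending on the last dose of a week, including the final prescribed interval.

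**3. One non-final prescribed interval of L calendar days.** By 10.2, last − first = L − 1, so the formula counts (L − 1) + 3 = L + 2 days. The excess is 2 days, or 2 × 3/7 = 0.86 dose.

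| L (days) | Doses due, L × 3/7 | Doses by formula, (L + 2) × 3/7 | Ratio for that interval |
|---|---|---|---|
| 14 | 6 | 6.86 | 87.5% |
| 28 | 12 | 12.86 | 93.3% |
| 56 | 24 | 24.86 | 96.6% |

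**4. A whole patient who misses nothing.** Assumptions: first dose and level changes on Mondays, and the dosing form ends on the last dose taken. The numerator sums strength × L. The denominator adds 2 days × strength for each non-final level only. The factor 3/7 cancels. Strengths are illustrative.
- No dose change: 100%.
- One change at Week 9, 200 to 250 mg, 28 weeks: (200 × 56 + 250 × 140)/(200 × 58 + 250 × 140) = 46,200/46,600 = 99.1%. Over 52 weeks: 88,200/88,600 = 99.6%.
- A change every 8 weeks, equal strengths, 28 weeks: 196/(196 + 3 × 2) = 97.0%. With escalation through 150, 200, 250 and 300 mg: 42,000/43,200 = 97.2%. Over 52 weeks, six changes, equal strengths: 364/(364 + 6 × 2) = 96.8%.
- Three reductions 2 weeks apart (200, 150, 120, then 100 mg), 28 weeks: 21,980/22,920 = 95.9%.
- A change every 4 weeks throughout, equal strengths: 196/208 = 94.2% (28 weeks) or 364/388 = 93.8% (52 weeks).

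**5. The other reading of the dosing form.** If the IP dosing form also ends on the day before the next level, numerator and denominator both count L + 2 days. Compliance is then 100%, but the total dose in 10.1 is too high by 0.86 dose per non-final interval (58/56, or 3.6%, for an 8-week level). The average weekly dose is too high as a result.

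**6. Mid-week change of level.** Suppose a level starts on Monday (Day 1), its last dose is on Monday (Day 57), and the new level starts on Wednesday (Day 59). The 10.1 formula counts 56 + 3 = 59 days and the 10.2 formula 57 + 3 = 60. The excess over the numerator is 1 day, and the ratio for that interval is 98.3%.

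**The case against.** The strongest objection is that the compliance bias rests on an end date the SAP does not give. Both sections use one expression, and if both forms end an interval the same way the excess cancels. The example leans that way: 7 January 2017 is a Saturday and 10 February a Friday. On a fixed weekly schedule that includes Saturday, Friday cannot be a dosing day when doses are at least 2 days apart. This stands as a limit on the compliance claim, although an illustrative example is weak evidence. It does not clear the formula, because on that reading the 10.1 exposure totals are wrong instead.

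It also rules out changing 10.2 alone. If the dosing form ends the day before the next level, that change would give 58/56 = 103.6% for an 8-week level and push compliant patients above 100%.

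A reader might infer from the interval ratios that a fully compliant patient scores 87 to 97%. The documents do not support that. Compliance is per patient over a period, and the final interval carries no excess. The 87.5% figure belongs to a single 2-week interval. A whole patient comes near it only with a new level every 2 weeks throughout: 196/(196 + 13 × 2) = 88.3% over 28 weeks. SAP 10.3 sets an 8-week minimum before further adjustment, and only reductions may come sooner. The maintenance rules (Protocol Appendix D, SAP 19.1) use a 4-week hemoglobin change and do not restate that minimum, but a change every 4 weeks still gives about 94%.

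A reader might also infer a spurious difference between arms, or patients falling widely below 85%. The number of changes may differ by arm, but the documents give no figure for this. Every scenario above stays in the 85 to 100% category.

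**Conclusion.** The point holds as a minor error in a stated rule. SAP 10.2 overstates prescribed drug by about 2 days (0.86 dose) per dose change, with nothing added for the final level. On either reading of the 10.1 end date one output is wrong:
- If the dosing form ends on the last dose taken, compliance is understated, by nothing without dose changes, under 1 point with one change and about 3 points with a change every 8 weeks. Early reductions cost slightly more.
- If it ends the day before the next level, total and average weekly dose are overstated instead.

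The patient-level figures assume a Monday/Wednesday/Friday schedule with Monday level changes. Mid-week changes shrink the excess over the numerator to 1 day.

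Only patients already near a category cut can move. With a change every 8 weeks over 28 weeks, the 85% cut is crossed only from true values between 85% and 85/0.970 = 87.6%. Compliance is summarized descriptively. Neither the Per-Protocol Set definition (SAP 5.3.3) nor the major deviation criteria (SAP Table 2) uses a compliance percentage, and no efficacy model uses it. The error in the 10.1 example is separate and does not depend on the end-date question.

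**What to change.** - In SAP 10.1, define the last day of a dose interval on the IP dosing form: either the last dose taken at that level or the day before the next level starts.
- In both 10.1 and 10.2, use (last − first + 1) where the interval ends the day before a new level. Keep +3 only where it ends on a dosing day, as for the final prescribed level. An 8-week level then gives 56 × 3/7 = 24 doses in numerator and denominator, and a patient who misses nothing shows 100% whatever the number of changes.
- Correct the 10.1 example: 792.9 mg by the printed formula if +3 is kept, or 750 mg with +1 if 02/10/2017 is the day before a new level. State which type of end date it illustrates.

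The cost is a short text edit and the matching change in the exposure and compliance programs, best made before the Week 28 tables are run. No new data are needed, unless the dosing form proves not to record the chosen end date.
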